9.1 Protection of participants

The study protocol has been approved by the ethics research committee registered with the Forum for Ethical Review Committees in Asia and the Western Pacific (FERCAP) (project number KE-FK-0674-EC-2023). The study will be conducted according to Indonesia's 2021 National Health Research and Development Ethical Guidelines and Standards by the Health Research and Development Ethics Committee and the Helsinki Declaration, revised in 2013.

9.2 Adverse events

We will look for the presence of any adverse events that might occur during each administration of CA Therapy, which include increased soreness, pain, numbness, and tingling. Any adverse event that is life-threatening or related to significant disability will be reported to the ethics research committee of the institution.

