Secondary Objectives	To evaluate the effect of acupressure and standardized curcuminoid from turmeric extract vs placebo at 3 weeks : 
 • Knee pain as measured by the VAS score • Joint stiffness and joint functional ability are assessed by the WOMAC score • The independence of the elderly as assessed by the Barthel Index • Quality of Life were measured by Respondents' satisfaction in carrying out daily activities based on indicators on the KOOS instrument
Study design	Randomized controlled trial, double-blind to assess efficacy, tolerability and safety combination of acupressure and curcuminoid versus placebo. Patients can be pre-screened for certain x-ray and laboratory parameters. Following a screening visit, eligible subjects will enter the wash-out for 1 week. After the wash-out period, eligible subjects will be randomized and treated for 3 weeks. The total duration of the study is up to 5 weeks
Population	Approximately 70 female and male patients ≥ 65 years old
Key Inclusion criteria	
 • Clinical diagnosis of osteoarthritis which confirmed by physical examination and x-rays • Experience pain with a Numeric Rating scale of 1-7 • Must be able to swallow capsules • Must be able to carry out mobility without assistance or with minimal assistance

Key Exclusion criteria	
 ● Parkinson's disease ● Dementia disease ● Psychosis disease ● New bone fractures ● Joint dislocations ● Cancer ● Rheumatic diseases other than osteoarthritis (rheumatoid arthritis) ● Undergoing joint replacement therapy. ● Analgesic dependent disease
Study treatment	
 ● Combination of Acupressure and Curcuminoid from turmeric extract ● Placebo
Efficacy assessments	
 ● Leukocytes ● Neutrophil Leukocyte Ratio ● Blood Sedimentation Rate ● Pain ● Secretion of COX-2 in blood ● Secretion of Endorphin hormones in blood
Key safety assessment	
 ● Physical examination ● Vital signs ● Monitoring of laboratory markers in blood
Others assessment	
 ● Quality of Life

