3.1 Study design

Randomized controlled trial, we will conduct a 2-arm, double-blind (patient and investigational blinded) to assess efficacy, tolerability and safety combination of acupressure and curcuminoid versus placebo.

Pre-Screening:

Patients can be pre-screened for certain x-ray and laboratory parameters. Following a screening visit, eligible subjects will enter the wash-out. After the wash-out period, eligible subjects will be randomized and treated for 3 weeks. The total duration of the study is up to 5 weeks.

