4.3 Eligibility test procedure

Radiographs will be used to assess participants for Osteoarthritis using the Kellgren and Lawrence criteria which divide Osteoarthritis from mild to severe. It should be remembered that at the beginning of the disease, the radiographic appearance of the joint still looks normal. According to Kellgren and Lawrence, radiologically, osteoarthritis is classified as follows:

- 1) Grade 0: Normal, no signs of osteoarthritis
- 2) Grade 1: Doubtful, without osteophytes, doubtful joint narrowing

3) Grade 2: Minimal, few osteophytes on the tibia and patella and the joint surface is asymmetrically narrowed.

4) Grade 3: Moderate, there are moderate osteophytes in several places, the joint surface is narrowed, and subchondral sclerosis appears.

5) Grade 4: Severe, presence of large osteophytes, complete narrowing of the joint surface, severe subchondral sclerosis, and joint surface damage.

Mini Mental State Examination (MMSE) test will be used to assess the patient's cognitive abilities. This is important to ensure that patients can understand the instructions in the treatment process and the outcome measurement process.

5 Randomization, allocation and blinding

A total of 70 eligible participants will be randomized to the group with curcuminoids capsules and acupressure (C+A; group 1) or the group with placebo and sham acupressure (P+S; group 2) via lottery randomization. Thereafter subjects will be randomly allocated to C+A and P+S group. The schematic CONSORT (Consolidated Standards of Reporting Trials) flow diagram for the study protocol is presented in Figure 1. Schematic CONSORT (Consolidated Standards of Reporting Trials) flowchart for the study.

[figure not shown]

Figure 1. Schematic CONSORT (Consolidated Standards of Reporting Trials) flowchart for the study

Determination of baseline characteristics for every participant will be done by the therapist through a standardized assessment form. During the baseline measurement, the following characteristics will be recorded: sex, age, body mass, pain characteristic, history of disease and medication use. The participant's participation schedule will be determined according to the SPIRIT (Standard Protocol Items: Recommendations for Interventional Trials) statement Figure 2. The primary and secondary outcome measures will be recorded before providing the intervention.

[figure not shown]
TIMEPOINT**	STUDY PERIOD								
	Enrolment	Allocation	Post-allocation			Close-out			

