		0	1 st week	2 nd week	3 rd week	1 st day	1 st week	2 nd week	Post 3 rd week
ENROLMENT:									
Eligibility screen	X								
Informed consent	X								
[Radiography and MMSE Test]	X								
Allocation		X							
INTERVENTIONS:									
[C+A Therapy]			X	X	X				
[P+S Therapy]			X	X	X				
ASSESSMENTS:									
[Demographic Details]	X								
[Inflammatory Marker]						X			X
[Endorphine]						X			X
[Quality of Life]						X	X	X	X

Figure 2. SPIRIT (Standard Protocol Items: Recommendations for Interventional Trials) recommended schedule for participation.

6 Intervention

After the standardized assessments and baseline measurements, the intervention will be conducted. Participants will be randomly assigned to the CA group or the PS group. For Acupressure Therapy and Sham Acupressure, each participant will be exposed to 3 therapy sessions per week of 20 minutes for 3 consecutive weeks. Participants will not be allowed to take any medication routinely during this time except for antihypertensive agents, thyroid medications, and antidiabetic drugs. To help participants adhere to the interventions, reminder messages will be sent before each session visit. For Curcuminoid capsules and placebo, Each participant will be exposed to taking capsules three times a day for 21 days.

Acupressure to perform CA, the patient is put in the supine position with legs straight. Prepare tools and materials such as a seat (or bed), warm water, olive oil, wet & dry tissue, towels. The therapist washes his hands, the client sits in a comfortable position. Teach patients breathing relaxation techniques to use during therapy. Give patients the opportunity to pray according to their respective beliefs. Make sure the client is relaxed and comfortable. Help remove the client's clothing or accessories that may hinder the acupressure action being performed, if necessary. Perform a client pain assessment. Wipe the client on the parts to be massaged with warm water that has been treated with a disinfectant solution using a small towel. Dry with a clean towel. Use cream or oil, do a warming massage with basic massage techniques, choose according to the client's condition (rubbing, squeezing, pressing) and stretching the patient's feet. Acupressure massage points are performed at ST34, ST36, Tai Xi Acupoint, GB34, SP 9, SP 8, EX-LE, EX-LE3, EX-LE4, EX-LE6, EX-LE7, EX-LE10

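### Section 9.2 ties the search for adverse events to CA Therapy: it makes no provision for the placebo plus sham arm and does not clearly cover the time between sessions

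*Combined protocol and SAP*

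**What the plan says.** Section 9.2 has two sentences. The first sets the search: "We will look for the presence of any adverse events that might occur during each administration of CA Therapy". Its examples are soreness, pain, numbness and tingling. The second covers onward reporting: "Any adverse event that is life-threatening or related to significant disability will be reported to the ethics research committee of the institution".

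Section 3.1 describes the trial as "double-blind (patient and investigational blinded) to assess efficacy, tolerability and safety combination of acupressure and curcuminoid versus placebo". Section 5 sets capsules plus acupressure against "the group with placebo and sham acupressure (P+S; group 2) via lottery randomization". Section 6 gives the arms short names: "Participants will be randomly assigned to the CA group or the PS group". The same section also uses CA for the hands-on procedure: "Acupressure to perform CA, the patient is put in the supine position with legs straight".

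Exposure has the same schedule in both arms. For real and sham acupressure, "each participant will be exposed to 3 therapy sessions per week of 20 minutes for 3 consecutive weeks". Active or placebo capsules are taken three times daily for 21 days (Section 6).

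Other text bears on safety. Section 6 ends its account of the acupressure procedure by asking the patient to report unusual sensations or discomfort. The Protocol summary lists physical examination, vital signs and "Monitoring of laboratory markers in blood" as key safety assessments. Section 11 allows further safety assessments case by case. The schedule in Figure 2 has no adverse-event row.

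**The concern.** A comparison of tolerability against placebo is interpretable only if events are looked for in the same way, and over the same period, in both arms. The one sentence that says when events will be looked for names the treatment of one arm. Staff who follow it as written would question CA patients and have no instruction for PS patients. An apparent excess of events under the combination could then be partly or wholly a product of the questioning.

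The period covered is a second weakness. Most capsule exposure falls between visits, and the examples in 9.2 are local symptoms that suit a massage session better than an oral product. A symptom that begins after a capsule taken at home might never be asked about.

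**Working it through.** The plan gives no figure to reproduce. The check compares the passages on two readings of CA Therapy and adds the exposure arithmetic.

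**Inputs (Section 6).** 3 sessions per week, 3 weeks, 20 minutes each; capsules 3 times a day for 21 days.

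**Exposure per patient.**
- Sessions: 3 × 3 = 9.
- Session time: 9 × 20 min = 180 min = 3 h.
- Treatment period: 21 × 24 h = 504 h. Share in session: 3 / 504 = 0.6%.
- Capsule times: 3 × 21 = 63. With at most one per session (assumed), at least 63 − 9 = 54 fall outside sessions: 54 / 63 = 86%.

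**What 9.2 covers on each reading.**

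| Reading of CA Therapy | CA arm | PS arm |
|---|---|---|
| Hands-on acupressure sessions | 3 of 504 h; at least 54 of 63 capsule times missed | sham sessions not named |
| Combined treatment of the CA arm | sessions, and possibly the 63 capsule intakes | nothing |

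The 0.6% and 86% apply to the 9.2 search on the first reading only. On the second, coverage of the CA arm may be much wider, and the contrast with PS grows. Neither reading provides for PS.

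**Does other text close the gap?**
- *Patient reports (Section 6).* No arm is named, and the phrase used for the period could mean one session or the three-week course. The request closes the hands-on procedure and sets no timing, form or recording.
- *Second sentence of 9.2.* Not limited by arm, but it concerns passing on life-threatening or disabling events, not finding events.
- *Safety list (Protocol summary).* Not limited by arm. Blood counts are scheduled through the inflammatory-marker row, but they do not capture symptoms. Physical examination and vital signs have no timing and no row in Figure 2.
- *Quality-of-life row (Figure 2).* KOOS is collected without limit by arm and asks about the previous week (Section 7), but it is a knee outcome instrument and not an adverse-event enquiry.
- *Case-by-case assessments (Section 11).* Not systematic.

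**Form of the bias.** If the true proportion with an event is p in both arms, and a share c of those patients is detected, the spurious difference is p × (c in CA − c in PS). It is zero when detection is equal. The documents give neither p nor c.

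**The case against.** The strongest reply is that this is a drafting slip. With patients and investigators blinded, staff should not know whom to question and would in practice ask everyone. Section 6 asks patients to report discomfort without naming an arm, the listed safety assessments are not restricted to one arm, and the formal objectives in Sections 2.1 and 2.2 contain no safety endpoint.

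Much of this stands, and it rules out several stronger inferences that a reader might draw:
- *That PS patients have no safety oversight, by intent.* The blinding, the scheduled blood counts and the reporting rule for grave events all speak against this.
- *That 9.2 is the only text soliciting symptoms.* The request in Section 6 also does so, though loosely.
- *That the time between sessions is uncovered in both arms on any reading.* If CA Therapy means the combined treatment, home capsule intakes in the CA arm may be included.
- *That the bias can be given a size.* Assuming a true proportion of 10% to 30% and every detection pattern from equal capture to full capture in CA and none in PS, the formula gives anything from 0 to 30 points. Those inputs are assumptions. No capture at all in PS is also hard to square with the blinding and the request in Section 6.

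What the reply does not supply is a written instruction to look for adverse events systematically in PS. If the wording is a slip, that is a reason to correct it. Safety is absent from the formal objectives, but it is in the stated purpose in the Protocol summary and in the design statement in Section 3.1.

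**Conclusion.** The point holds in this form: the only section on adverse events names CA Therapy, makes no provision for PS, and leaves the time between sessions unclear, in a trial meant to assess tolerability and safety against placebo. The missing provision for PS does not depend on how CA is read. The between-session gap does: 0.6% of treatment time searched and at least 86% of capsule times missed apply only if CA Therapy means the hands-on sessions, and the 86% also assumes at most one capsule time per session.

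A between-arm difference in events could reflect how they were sought if 9.2 is followed literally. Whether staff would do so is unknown, and the size of any distortion cannot be estimated from the documents. The wording should be changed. Confidence is medium, because the intent may well have been to question both arms alike.

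**What to change.** Reword Section 9.2, and reconcile it with the safety list in the Protocol summary and the patient-report request in Section 6, so that:
- adverse events are sought in both arms, with the same questions and the same form, at each of the nine planned session visits;
- each enquiry covers the session and the time since the last visit, including symptoms after capsules.

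Add an adverse-event row to Figure 2. In Section 9.3, which gives tests and summaries for means or medians but none for patients with an event, add the number and proportion with at least one event per arm, reported descriptively.

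The cost is a written amendment with ethics approval (Section 11.1), one form, and a few minutes at visits already planned. Patients would have to recall a few days: three visits a week means 7 / 3, or about 2.3 days, between visits on average. Precision will be low. With 35 per arm (70 randomised, equal split assumed) and equal counts of 4, 7 or 10 patients with an event per arm (about 11%, 20% and 29%), the Newcombe 95% interval for the difference is about ±16, ±19 and ±21 points. The result would describe safety and would not establish it.

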9.3 Data analysis

The data collected will be analyzed by the secondary researcher. Descriptive statistics will be used to evaluate the baseline characteristics of participants. The normality of the collected data will be established using the Shapiro–Wilk test. Based on data normality, descriptive statistics will be expressed as mean \pm standard deviation or median (interquartile range). Within-group comparisons will be conducted using the Wilcoxon signed-rank test or a paired t test. Similarly, the Mann–Whitney U test or an independent t test will be used for between-groups comparisons. The level of significance will be set at 0.05.

9.4 Data management

Data collected will be kept confidential throughout the study duration and will be discarded after 5 years. Initial documentation of data will be performed through printed data-collection forms, which will later be managed and transcribed into electronic format and stored on a desktop computer without an internet connection (to help prevent unauthorized data access) for further analysis. Data will be overseen by the chair of the student project committee of the institute

10. Ethical considerations

10.1 Regulatory and ethical compliance

This clinical study was designed and shall be implemented, executed and reported in accordance with the ICH Harmonized Tripartite Guidelines for Good Clinical Practice, with applicable local regulations (including Indonesia's 2021 National Health Research and Development Ethical Guidelines and Standards by the Health Research and Development Ethics Committee and with the ethical principles laid down in the Declaration of Helsinki.

10.2 Informed consent procedures

Eligible patients may only be included in the pre-screening or in the study after providing written (witnessed, where required by law or regulation), IRB/IEC-approved informed consent, or, if incapable of doing so, after such consent has been provided by a legally acceptable representative(s) of the patient. In cases where the patient's representative gives consent, the patient must be informed about the pre-screening and/or the study, as applicable, to the extent possible given his/her understanding. If the patient is capable of doing so, he/she must indicate assent by personally signing and dating the written informed consent document or a separate assent form. Informed consent must be obtained before conducting any pre-screening or study-specific procedures (e.g. pre-screening assessments/all of the procedures described in the protocol). The process of obtaining informed consent must be documented in the patient source documents.

Novartis will provide to investigators in separate documents proposed pre-screening and study informed consent forms that comply with the ICH GCP guideline and regulatory requirements and are considered appropriate for pre-screening and for participation in the study. Any changes to the proposed consent forms suggested by the investigator must be agreed to by Novartis before submission to the IRB/IEC, and a copy of the approved version must be provided to the Novartis monitor after IRB/IEC approval.

Women of child bearing potential must be informed that taking the study treatment may involve unknown risks to the fetus if pregnancy were to occur during the study and agree that in order to participate in the study they must adhere to the contraception requirement for the duration of the study. If there is any question that the patient will not reliably comply, they must not be entered in the study.

10.3 Responsibilities of the investigator and IRB/IEC

Before initiating a trial, the investigator/institution must obtain approval/favorable opinion from the Institutional Review Board/Independent Ethics Committee (IRB/IEC) for the trial protocol, informed consent form(s), consent form updates, patient recruitment procedures (e.g., advertisements) and any other written information to be provided to patients. Prior to study start, the investigator is required to sign a protocol signature page confirming his/her agreement to conduct the study in accordance with these documents and all of the instructions and procedures found in this protocol and to give access to all relevant data and records to monitors, auditors, Quality Assurance representatives, designated agents of IRBs/IECs, and regulatory authorities as required. If an inspection of the clinical site is requested by a regulatory authority, the investigator must inform IRBs/IECs immediately that this request has been made.

10.4 Publication of study protocol and results

The key design elements of this protocol will be posted in a publicly accessible database such as clinicaltrials.gov. In addition, upon study completion and finalization of the study report the results of this trial will be either submitted for publication and/or posted in a publicly accessible database of clinical trial results.

11. Protocol adherence

This protocol defines the study objectives, the study procedures and the data to be collected on study participants. Additional assessments required to ensure safety of patients should be administered as deemed necessary on a case by case basis. Under no circumstances is an investigator allowed to collect additional data or conduct any additional procedures for any research related purpose involving any investigational drugs under the protocol.

Investigators ascertain they will apply due diligence to avoid protocol deviations. If an investigator feels a protocol deviation would improve the conduct of the study this must be considered a protocol amendment, and unless such an amendment is agreed upon by the IRB/IEC and health authorities, where required, it cannot be implemented.

